## **10.8 Blood samples**

Clinical chemistry has to be performed according to table 1 with measurement of creatinine (traceable standardized method), sodium, and potassium at every visit. HbA1c (DCCT-aligned method or IFCC) has to be measured at Screening and every periodic visit in both groups. Lipids (cholesterol, HDL, LDL, and triglycerides) have to be measured at least every year in all patients.

All blood samples are to be analysed locally.

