## **13.3 Documentation and reporting of AE**

### **13.3.1 Documentation requirements**

#### **13.3.1.1 AEs**

AE will be collected by the investigator either based on the information provided spontaneously by the patient or evaluated by non-suggestive questions.

The following information is necessary:

- Type of AE (disease, symptoms)
- Classification (serious vs. nonserious)
- Start and termination date of the AE
- Grading of AE-intensity (grade 1-5). The descriptions and grading scales found in the revised NCI CTCAE version 4.0 will be used for adverse event reporting.
- Causality to the study drug
- Measures taken with regard to study medication and treatment of the AE
- Outcome of the AE

The AE documentation period for this trial begins upon first administration of the IMP. In case of continuation of any AE the documentation period will be prolonged until all AEs are resolved or until the investigator assesses the adverse events as "chronic" or "stable".

Site investigator is responsible for monitoring the safety of patients enrolled into the study at the study sites. All AEs will be documented in the patient's medical record and managed according to standard practice.

The following AEs will additionally be documented in the eCRF:

- AEs leading to study drug discontinuation and/or withdrawal
- Serious AEs (SAEs, see Section 13.1.3)
- AEs related to cardiovascular and/or renal disease
- AEs related to retinopathy (and corresponding laser treatment)

- Laboratory abnormalities suspected by the investigators to be related to the study drug including the potassium and sodium value

At each patient visit the investigator will review the patient's medical record and determine if there have been any serious adverse events (SAEs) and/or AEs to be documented.

All eCRF-documented AEs, SAEs and laboratory abnormalities must be graded for severity and relationship to study drug and will be coded using the MedDRA via MARVIN.

Documentation of AEs must be performed in a timely manner on the respective AE forms in the eCRF.

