## **13.3.2 Reporting requirements**

### **13.3.2.1 Reporting period**

The reporting period for AEs and SAEs begins with the first application and ends 30 days after the last application of the IMP.

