#### **14.6 Criteria for discontinuation**

A participant must be discontinued in the IMP treatment if any of the following is present:

- Female patients in the intervention study who become pregnant, intend to become pregnant or do not use adequate birth control (according to inclusion criteria 7, in section 7.1).
- Experience of research-related injury or unacceptable side effects to the study medication.
- Safety considerations assessed by the investigator
- Treatment with Lithium (ATC: N05AN).
- Treatment with potassium sparing diuretics (ATC: C03D, C03E).
- Confirmed eGFR below 15 ml/min/1.73 m^2.
- Confirmed elevated liver enzyme (ASAT and/or ALT) 3 times above normal range.

Discontinued patients will be offered tests corresponding to the final study visit. Data on all patients will be included in the study and will be used in safety analysis.

After discontinuation of study medication in the randomized population, observation should continue with visits as planned in the observational group (if the patient accepts), or if that is not possible/acceptable, evaluation of vital status and development of endpoints should be evaluated through registries, information of hospitals and GPs, or interviews with the patient as appropriate and possible in order to monitor development of endpoints in all included patients as thoroughly as possible, provided that the patient agrees.

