4.3.3 Intention to treat cohort

All participants with a valid proteomic score with a high-risk pattern who was provided with study medication

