6.1.2 Secondary outcome

- A. Comparison of composite fatal and non-fatal cardiovascular outcome (MI, stroke, CABG, PTCA, hospitalization for heart failure and CVD) and all-cause mortality during the study.
- B. Comparison of incidence of retinopathy and frequency of laser treatment. Data collected from self-reported AEs.
- C. In addition to the categorical analysis of UACR, an analysis will be performed with changes in geometric mean of UACR throughout the study period in all patients by assessing the slope of albuminuria changes and absolute changes from inclusion to end of trial.
- D. Development of microalbuminuria (UACR >30 mg/g) in at least one morning void urine sample will be used as a secondary outcome instead of confirmed microalbuminuria.
- E. Development of macroalbuminuria (UACR >300 mg/g) in 2 out 3 first morning void urine samples).
- F. For patients with eGFR ≥ 60 ml/ min/ 1.73 m² at baseline, development of eGFR <60 ml/min/1.73m².
- G. Development of CKD stage 4 (eGFR <30 ml/min/1.73m²).
- H. Change in eGFR (slope) from baseline and from three-month post-baseline to end of study.
- I. Change in eGFR (40 % reduction) from baseline and from three-month post-baseline to end of study.
- J. Safety: Adverse Events and Serious Adverse Events. Adverse Events leading to death or discontinuation of study medication and/or withdrawal.
- K. Event of hyperkalaemia with potassium level in plasma ≥ 5.5 mmol and/or ≥ 5.8 mmol in serum at any time point.

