6.3.2.2 Analysis of secondary endpoints

Based on a 2x2 table included the primary endpoint (event/ event free) vs. treatment allocation (active/ placebo) we will calculate numbers needed to treat and tested for significance using Chi-square test.

For Cox-regression models both unadjusted and adjusted using treatment allocation as determinant. Adjustment for age, gender, HbA_{1c}, systolic blood pressure, retinopathy, study site, eGFR and UACR at baseline will be conducted for both primary and secondary endpoints (see section 6.1.1 and 6.1.2, excluding 6.1.2 C, H and J).

For further clarification of the added value for discrimination, the rIDI will be calculated for all above described Cox-regression models with a significant HR for treatment allocation in the unadjusted model for each endpoint.

For safety outcome (section 6.2.1 J) only AE/SAE with the term hypotension, hyperkalaemia or gynaecomastia will be analysed using chi-square test.

To evaluate changes in UACR and eGFR over time (outcome measurement C and H in section 6.2.1) a linear mix model will be applied with adjustment for eGFR and UACR at baseline.

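### Three adverse-event terms are compared as crude proportions although new events are collected only to 30 days after the last dose, so unequal stopping of drug would understate harm in the arm that stops more

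*SAP*

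**What the plan says.** **Collection.** Protocol 13.3.2.1: "The reporting period for AEs and SAEs begins with the first application and ends 30 days after the last application of the IMP". Protocol 13.3.1.1 lengthens this only for events already under way: "In case of continuation of any AE the documentation period will be prolonged until all AEs are resolved" or are judged chronic or stable. New events get no extension.

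**Follow-up.** Protocol 14.6: "After discontinuation of study medication in the randomized population, observation should continue with visits as planned in the observational group", if the patient accepts. Appendix 1 (24.5) keeps patients who stop drug in the study to its full duration.

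**Analysis.** SAP 6.3.2 is assigned to the intention-to-treat cohort, defined in 4.3.3 as "All participants with a valid proteomic score with a high-risk pattern who was provided with study medication". For outcome J, "only AE/SAE with the term hypotension, hyperkalaemia or gynaecomastia will be analysed using chi-square test". No at-risk window or person-time is given. The Cox models cover "both primary and secondary endpoints (see section 6.1.1 and 6.1.2, excluding 6.1.2 C, H and J"), so J has no time-to-event analysis. Protocol 15.8 describes exposure by arm but does not use it as a denominator.

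**Hyperkalaemia has a second route.** Outcome K in SAP 6.1.2 is "Event of hyperkalaemia with potassium level in plasma ≥ 5.5 mmol and/or ≥ 5.8 mmol in serum at any time point". It is not among the outcomes excluded from the Cox models.

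**The concern.** A chi-square on proportions treats every patient as watched for the same time. Here a patient who stops drug after six months, in a study lasting 104 to 230 weeks, can contribute a new adverse event for only about seven months, yet stays in the denominator as if followed to the end.

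If stopping is similar in both arms, little is lost in the comparison. If it is more frequent on spironolactone, the active arm has less time in which an event can be recorded, and the comparison is pulled towards too little harm.

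These are the only adverse-event terms that the SAP tests between arms. The treatment is preventive and is given to patients with normal albumin excretion, so an understated harm would weigh on the benefit-risk judgement.

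**Working it through.** **The plan's own figure.** The plan states no figure for the safety comparison. Its one computed figure, 129 per arm, reproduces: (1.96 + 0.8416)² × (0.40×0.60 + 0.24×0.76) / 0.16² = 129.5. It supplies only the planned 150 per arm used for power below.

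**Inputs from the documents.** Follow-up F is 2.0 to 4.4 years (Protocol synopsis). The window closes d = 30 days = 0.082 year after the last dose (Protocol 13.3.2.1).

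**Assumptions, not in the documents.** Placebo event risk q is 5% or 10% over full follow-up. The proportion p stopping drug is 10% on placebo and 10% to 40% on spironolactone. Event and stopping times are exponential, and stopping is unrelated to the term tested.

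**Formulas.** Event hazard h = −ln(1−q)/F, multiplied by the true ratio on spironolactone. Stopping hazard s = −ln(1−p)/F. Window W = min(stopping time + d, F). Mean window = d + (1 − e^(−s(F−d)))/s. Crude proportion = 1 − E[e^(−hW)].

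**Worked case.** F = 3.2 years, q = 10%, stopping 10% against 30%.
- s = 0.0329 and 0.1115 per year. Mean window = 3.045 and 2.716 years, ratio 0.89.
- True ratio 1: crude 9.53% on placebo and 8.51% on spironolactone, ratio 0.89.
- True ratio 2: crude 16.23% on spironolactone, ratio 16.23/9.53 = 1.70.
- Chi-square power at true ratio 2, 150 per arm: 58% with equal stopping, 41% with 10% against 30%.

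**Range over F = 2.0 to 4.4 years and q = 5% or 10%.**

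| Stopping, placebo vs spironolactone | Window-time ratio | Crude ratio, true 1.0 | Crude ratio, true 2.0 |
|---|---|---|---|
| 10% vs 10% | 1.00 | 1.00 | 1.90–1.95 |
| 10% vs 20% | 0.95 | 0.95 | 1.80–1.85 |
| 10% vs 30% | 0.89–0.90 | 0.89–0.90 | 1.70–1.75 |
| 10% vs 40% | 0.83–0.84 | 0.83–0.84 | 1.59–1.64 |

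The first row's shortfall from 2.0 is not caused by the window. A risk ratio falls short of a hazard ratio of 2 even with complete capture: (1 − 0.90²)/0.10 = 1.90 and (1 − 0.95²)/0.05 = 1.95. The effect of unequal stopping is the further fall down the column.

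**A second stopping model.** Follow-up uniform over 104 to 230 weeks, stopping uniform over weeks 2 to 78, 3 events per 100 patient-years on placebo, 15% stopping on placebo. The window covers 89% of placebo follow-up, and 82% or 74% of active follow-up if 25% or 35% stop. A true 1.0 appears as 0.92 or 0.84, and a true 2.0 as about 1.75 or 1.60. First events per window patient-year give the true ratios back.

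**Which stopping matters.** Take the second model with 15% background stopping in both arms, and let the tested event itself trigger stopping. Stopping rises to about 30% against 23% at a true ratio of 2, but the crude ratio stays at about 1.9, because the triggering event is counted. Now let gynaecomastia alone drive stopping (17% or 27% on active, 2% on placebo). A true hypotension ratio of 2.0 then appears as about 1.75 or 1.66. The loss falls on the other terms.

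**The case against.** **Unequal stopping is assumed.** No rate by arm is given, and the synopsis expects equal drop-out. This stands as far as size is concerned. But drop-out is not the same as stopping drug. Protocol 11.3 lists gynaecomastia and hyperkalaemia as spironolactone effects, and 14.6 and Appendix 1 provide for stopping drug for unacceptable side effects and for raised potassium. More stopping on spironolactone is plausible, though not established.

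**A reader might infer that the arm that stops more looks safer by construction.** The documents do not support that. The distortion needs unequal stopping, an event that causes stopping is itself recorded, and a true doubling still appears as about 1.6 or more in these scenarios. A crude ratio below 1 arises only when there is little or no true excess.

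**A reader might infer that no other safety outcome is tested.** That is also wrong. Outcome K is laboratory-based, covers any time point and falls under the Cox models, and Protocol 10.8 requires "measurement of creatinine (traceable standardized method), sodium, and potassium at every visit". This largely protects hyperkalaemia, though imperfectly: after stopping, visits follow the observational group's annual schedule instead of every 13 weeks.

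**Selective recording may work the other way.** Protocol 13.3.1.1 sends only listed categories to the eCRF, among them events leading to discontinuation. A non-serious gynaecomastia may be recorded mainly when drug is stopped, which would raise the count in the arm that stops more. This stands, is not quantified, and is not cured by person-time.

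**Crude incidence is a usual safety summary, and other tables would reveal differential stopping.** True: Protocol 15.8 summarises exposure and discontinuations due to adverse events by arm. A reader would see the imbalance but could not correct the comparison from it.

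**Conclusion.** The point holds as a conditional dilution of harm. Collection ends 30 days after the last dose, the analysis ignores time at risk, and outcome J has no time-to-event analysis. If spironolactone is stopped 10 to 30 percentage points more often than placebo, its crude proportions are understated by about 5% to 17% (relative) under equal hazards, and a true ratio of 2.0 appears as about 1.6 to 1.85. With equal stopping the window adds almost nothing.

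These sizes rest on assumed stopping rates, constant hazards, and stopping unrelated to the term tested. Hypotension and gynaecomastia are the most exposed. For gynaecomastia the net direction is uncertain, because selective eCRF entry may offset the loss. The change is worth making because it is cheap and gives a better estimate, not because the planned test is bound to mislead.

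**What to change.** In SAP 6.3.2.2, for hypotension, hyperkalaemia and gynaecomastia:

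- Define the at-risk window as first dose to 30 days after last dose, or end of study if earlier.
- By arm, report patients with a first event, patient-years at risk, first events per 100 patient-years, and a Cox or rate ratio with 95% CI.
- Tabulate window patient-years by arm.
- Keep the crude percentage and chi-square as descriptive.
- State that the estimate assumes stopping is non-informative for the term analysed, and that selective eCRF recording is not corrected.

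SAP 6.2 rules out any censoring and needs an exception here, since the analysis censors at the end of the window. The reference in 6.3.2.2 to outcome J in section 6.2.1 should read 6.1.2.

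The cost is SAP wording and one extra table. Event start dates are already required by Protocol 13.3.1.1, and the reporting rule already presupposes first and last dose dates. No visit, treatment rule or data item changes.

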6.3.2.3 Sensitivity analysis

In a forest plot each baseline continuous variable: Age, HbA_{1c}, systolic blood pressure, eGFR and UACR will be divided based on the median value and tested for heterogeneity between treatment allocation. Of the categorical variables we will evaluate the effect of: Gender, and presence of retinopathy at baseline also in a forest plot. We expect the largest effect of active treatment in participants with known risk factors of overt kidney disease (high age, HbA_{1c}, systolic blood pressure, UACR and low eGFR, male gender and presence of retinopathy).

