3.4 Sample size

The expected relative proportions of diabetes type 2 patients developing microalbuminuria in our study population are: 24% in patients at high-risk for diabetic nephropathy in the treatment group, 40% in those patients at high-risk for diabetic nephropathy in the placebo group and 8.5% in those therapy-naive patients at low-risk for diabetic nephropathy. Using the sample size formula for two proportions test ($\alpha= 0.05$ $\beta=0.80$), randomized (1:1), $n=129$ in each arm of the intervention group are required. To account for an expected drop-out rate of 10 %, we plan to include 300 participants in the intervention part of the study.

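### The only treatment-by-covariate tests for age, HbA1c, systolic BP, eGFR and UACR use median halves; a continuous interaction would be more efficient, though still weak at the expected event count.

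*SAP*

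**What the plan says.** SAP 6.3.2.3, the sensitivity analysis of the intervention study, names the variables: "In a forest plot each baseline continuous variable: Age, HbA_{1c}, systolic blood pressure, eGFR and UACR". These "will be divided based on the median value and tested for heterogeneity between treatment allocation". Gender and retinopathy are added to the forest plot as categorical variables. The section also states an expectation: "We expect the largest effect of active treatment in participants with known risk factors of overt kidney disease". In parentheses it lists high values of age, HbA1c, systolic BP and UACR, low eGFR, male gender and retinopathy.

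No other section tests these five variables as continuous modifiers of the treatment effect:

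- SAP 6.3.2.2 and 6.4 use them as adjustment covariates.
- The Cox interaction in SAP 6.3.1.3 is between the high- and low-risk strata of the observational cohort, not between treatments.
- Protocol 15.7 plans exploratory analyses of baseline variables as predictors of endpoints, not of treatment response.
- The Protocol synopsis and Section 3 say only that age and gender effects on the treatment effect will be considered.
- Protocol 15.6 enters baseline UACR as a log10-transformed continuous covariate, so a continuous form of that variable is already in the plan.

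The documents give no power and no expected shape of effect modification for these tests.

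**The concern.** A median split treats patients just either side of the median as different, and patients at the median and at the extreme of the same half as alike. When the treatment effect varies smoothly with the covariate, this discards information that has already been collected. The loss falls on tests that are short of events to begin with.

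At stake is how well a secondary question is answered: whether the benefit of spironolactone differs with baseline risk. A less efficient test gives a wider interval and a lower chance of detecting a gradual change in effect. The validity of the test and the primary comparison in SAP 6.3.2.1 are not at stake.

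**Working it through.** **Inputs from the documents.** SAP 3.4 expects events in "24% in patients at high-risk for diabetic nephropathy in the treatment group" and "40% in those patients at high-risk for diabetic nephropathy in the placebo group", with α = 0.05, 80% power (written there as β), 1:1 allocation, 129 per arm, and 300 randomised to allow for 10% drop-out.

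**The plan's own figure.** Two-proportion formula with unpooled variance, two-sided:
n = (1.960 + 0.842)² × (0.40×0.60 + 0.24×0.76) / (0.40 − 0.24)² = 7.849 × 0.4224 / 0.0256 = 129.5 per arm. The stated 129 is reproduced to rounding. The documents give no corresponding figure for the heterogeneity tests.

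**Expected events.** The average proportion is (24% + 40%)/2 = 32%. With 300 patients: 300 × 0.32 = 96. With 10% lost (270 patients): 270 × 0.32 = 86. Under proportional hazards the implied overall HR is ln(0.76)/ln(0.60) = 0.54.

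**Information kept by the split.** This is the squared correlation between the covariate and its above-median indicator. For a normal covariate it is 2/π = 63.7%, a loss of 36.3%. For testing a linear interaction, 96 events then count as 96 × 0.637 = 61. Assumed distributions, truncated at the eligibility limits where there is one, give similar losses:

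- age (mean 62, SD 9): 34%
- eGFR (mean 85, SD 18): 35%
- systolic BP (mean 135, SD 13): 32%
- log UACR (medians 5 to 12 mg/g, log-SD 0.6 to 1): 34–36%

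More generally, the loss runs from 25% for a uniform covariate to over 50% for a strongly skewed one.

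**Power.** Let b be the interaction in log-HR per SD and D the number of events.

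- Continuous: SE = 2/√D, so power = Φ(|b|√D/2 − 1.96).
- Split: the half means differ by 2√(2/π) = 1.596 SD and the SE between halves is 4/√D, so power = Φ(1.596|b|√D/4 − 1.96).

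For b = −0.4 and D = 96 (√D = 9.798), the continuous test has Φ(1.960 − 1.960) = 50%. The split has Φ(1.564 − 1.960) = 35%.

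| b per SD (ratio of HRs) | 96 events: continuous / split | 86 events: continuous / split |
|---|---|---|
| −0.2 (0.82) | 16% / 12% | 15% / 11% |
| −0.3 (0.74) | 31% / 22% | 29% / 20% |
| −0.4 (0.67) | 50% / 35% | 46% / 32% |
| −0.6 (0.55) | 84% / 65% | 80% / 60% |

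**Simulation check.** Cox simulations with 300 patients and a normal covariate (1,500 trials per setting) gave 30% / 20% at −0.3 and 80% / 58% at −0.6. A second set, with follow-up uniform on 2 to 4.4 years (800 trials per setting), gave 50% / 32% at −0.4 and 78% / 59% at −0.6. With no interaction, rejection was between 4.5% and 5.8% for both methods.

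**How large these interactions are.** With HR 0.54 at the covariate mean (log-HR −0.621), b = −0.6 puts the HR above 1 for patients below −0.621/0.6 = −1.04 SD, about 15% of the sample. With b = −0.4 the HR at −2 SD is exp(−0.621 + 0.8) = 1.20. Nothing in the documents suggests modification of that size, so the smaller rows of the table matter at least as much as the larger ones.

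**The opposite case.** In one simulation with the true effect a step exactly at the median, the split had 43% power and the continuous test 33%.

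**The case against.** **No trend is stated.** A reader might infer that the SAP predicts a graded trend that the split fails to test. SAP 6.3.2.3 uses high-versus-low language and lists the continuous variables beside two binary ones, so a median split does answer the expectation as worded. The log-linear shape behind the power comparison is an assumption of this review. This objection stands.

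**The event count, not the split, is the main limit.** At −0.2 per SD the gain is about 4 percentage points, and both tests would usually miss the interaction. This also stands.

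**A false report of no heterogeneity.** A reader might infer that a real gradient would probably be reported as absent because of the split. The figures do not support this as a general claim. At −0.6 per SD the split still detects the interaction in about 59% of simulated trials, while at −0.4 the continuous test itself misses half.

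**Data-dependent cut points.** A reader might also see the sample median as an invalid cut. It is a pre-specified rule that ignores outcomes and prevents searching for a cut point, and the type I error is close to 5%. The cost is in efficiency only.

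**Little depends on it.** The tests sit under sensitivity analysis, and the sample size, primary comparison and adjusted Cox models do not use them. That limits the weight of the point. It does not remove it, because these are the only planned tests of effect modification by the five variables.

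**Conclusion.** The point holds as a minor matter of efficiency. For a roughly symmetric covariate and a log-linear interaction, testing on median halves gives up about a third of the information. At 96 expected events that is roughly 15 to 18 percentage points of power at −0.4 log-HR per SD (50% against 32–35%) and about 4 points at −0.2 (16% against 12%).

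These figures rest on the event proportions in SAP 3.4, on assumed covariate distributions and on the assumed shape; the documents give neither of the last two. Even with the change, 80% power at 96 events requires a ratio of HRs of about 0.56 per SD, compared with about 0.49 for the split. The heterogeneity analysis therefore remains exploratory whichever form is used.

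**What to change.** Keep the median-split forest plot for display. Add to SAP 6.3.2.3 that, for each of the five continuous variables, the interaction estimate, its 95% CI and the heterogeneity p-value come from a Cox model with treatment, the continuous covariate and their product. UACR should be log-transformed, as in Protocol 15.6. Label the results exploratory: with seven variables tested at 0.05, the chance of at least one false positive would be 1 − 0.95⁷ = 30% if the tests were independent.

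The cost is a sentence or two in the SAP and five model fits on data already collected. The continuous test assumes a log-linear interaction and loses some power if the true effect is a step at the median. The shape should therefore be checked, either with an added non-linear interaction term or by comparing the model's predictions with the split-half estimates. Two half-sample points cannot show curvature on their own, and a curve fitted from a linear interaction is log-linear by construction, so neither plot alone is a check. With 86 to 96 events the check will be rough, and the SAP should say so.
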